**Table 3 Objectives and Endpoints**

Objective	Endpoint/Variable
Exploratory Objectives	Exploratory Endpoint/Variable
[Redacted Content]	

AE = adverse event; AUClast = area under the concentration-time curve from time 0 to last measurable time point; BSC = best supportive care; [Redacted] Cmax = maximum observed concentration; COVID-19 = coronavirus disease 2019; CRP = C-reactive protein; [Redacted] PK = pharmacokinetic(s); PPI = proton-pump inhibitor; SAE = serious adverse event; SARS-CoV-2 = severe acute respiratory syndrome coronavirus 2; [Redacted]

## 4 STUDY DESIGN

### 4.1 Overall Design

This is an open-label, multi-dose study to evaluate the PK, and safety and tolerability of acalabrutinib suspension, when coadministered with a PPI, in participants with confirmed SARS-CoV-2 infection requiring hospitalization due to respiratory failure (as defined in Section 8.1.1.1) attributable to COVID-19 pneumonia and who have an NG tube in place. Approximately 20 participants will be included to ensure at least 16 participants are evaluable. Participants are considered evaluable if they have an evaluable PK profile, ie: (1) complete PK Visit 2 assessments; (2) receive active treatment; and (3) do not have unavailable or incomplete data that may influence the PK analysis.

In addition to BSC, participants will receive acalabrutinib suspension (ie, acalabrutinib 100 mg suspension in COCA-COLA delivered via NG tube) bid for 14 days (a maximum of 28 doses). Best supportive care is per discretion of the Investigator and institutional guidelines. Standard NG tubes supplied by the hospital will be used. Nasogastric tube placement in the stomach will be confirmed by chest x-ray.

To assess the effect of PPIs, all participants must be receiving treatment with a PPI at the start of the study. Treatment with a PPI can begin at any time prior to enrollment, provided participants have received PPI treatment for at least 24 hours prior to the first dose of acalabrutinib suspension (Figure 1). Any PPI is permitted, provided it meets the minimum equivalent daily dose of 20 mg rabeprazole (Appendix H). Participants must be on this dosage

of PPI at the start of the study. They may be weaned off PPIs during the study if medically appropriate.

Blood samples for plasma PK assessment of acalabrutinib and its metabolite (ACP-5862) will be collected at pre-dose and 0.5, 1, 2, 4, 6, and 12 hours following treatment with acalabrutinib suspension as described in Table 4 below and illustrated in Figure 1. Note that the sample at 12 hours must be collected prior to the subsequent acalabrutinib dose (for trough PK sample).

**Table 4 Pharmacokinetic Sampling Relative to Start of Proton-pump Inhibitor Treatment**

PK Visit	Description	Rationale
PK Visit 1	First PK sampling will occur on Day 1 (ie, first dosing day for acalabrutinib suspension)	Allows an early assessment of acalabrutinib and ACP-5862 PK in participants receiving acalabrutinib suspension via NG tube
PK Visit 2	Second PK sampling will occur a minimum of 4 days after the start of PPI treatment, irrespective of the timing of NG tube placement and any time after 2 doses of acalabrutinib suspension have been given (ie, PK sampling can begin prior to the third dose, or anytime thereafter) PK Visit 2 can occur as early as Day 2 (if participant has been on a PPI for $\geq 4$ consecutive days prior to receiving the third acalabrutinib dose), and up to Day 4 (if participant initiated PPI treatment 24 hours prior to receiving the first dose of acalabrutinib on Day 1)	PPI exposure must occur for 4 consecutive days to reach the maximum PPI on-target effect PK sample can commence at any point after the second dose of acalabrutinib suspension to ensure steady-state levels of the active metabolite and maximal [REDACTED] [REDACTED] [REDACTED] has been reached
PK Visit 3	Third PK sampling will occur 3 days after PK Visit 2, OR on the last day the participant receives acalabrutinib treatment, whichever comes first	Allows an additional opportunity to assess the steady state PK of acalabrutinib and ACP-5862 PK following delivery of acalabrutinib suspension via NG tube

[REDACTED] NG = nasogastric; PK = pharmacokinetic(s); PPI = proton-pump inhibitor.

Safety assessments, including AE reporting, will be performed through 28 ( $\pm 3$ ) days after the last dose of the acalabrutinib suspension.

## 4.2 Scientific Rationale for Study Design

This open-label, multiple-dose study is intended to evaluate the PK, and safety and tolerability of acalabrutinib suspension delivered via NG tube, when coadministered with a PPI, to inform supportive care in COVID-19 patients.

Since PK and safety assessments are the primary objectives of the study, an open-label design was selected. The study will be conducted in participants with confirmed SARS-CoV-2 infection requiring hospitalization due to respiratory failure (as defined in Section 8.1.1.1)

attributable to COVID-19 pneumonia and who have an NG tube in place.

### **4.3 Justification for Dose**

The dose and regimen of acalabrutinib in this study is 100 mg bid (approximately every 12 hours apart), which is consistent with the recommended dosing regimen of acalabrutinib for clinical use (CALQUENCE 2019). The dose of 100 mg acalabrutinib to be administered in this study in hospitalized COVID-19+ patients requiring ventilator support is not anticipated to exceed the acalabrutinib exposure or  $C_{max}$  reported in patients with hematologic malignancies. Thus, based on the results from previous clinical studies in hematologic malignancies, the 100-mg dose should provide sufficient plasma exposure for the PK analysis of acalabrutinib and its active metabolite, ACP-5862.

The 14-day treatment duration in this study was selected based on balancing the course of the illness and minimizing exposure to an immunosuppressive agent.

### **4.4 End of Study Definition**

The end of the study is defined as the last expected visit/contact of the last participant in the study.

A participant is considered to have completed the study if he/she has completed his/her last scheduled procedure shown in the SoA (Table 1).

All participants who discontinue study intervention for any reason other than withdrawal of consent, loss to follow-up, or death will have a safety follow-up assessment 28 ( $\pm$  3) days after the last dose of acalabrutinib, as outlined in Section 1.3.

The study may be stopped if, in the judgment of the Sponsor, participants are placed at undue risk because of clinically significant findings.

Refer to Appendix A 5 for guidelines for the dissemination of study results.

## **5 STUDY POPULATION**

Prospective approval of protocol deviations to recruitment and enrollment criteria, also known as protocol waivers or exemptions, is not permitted.

### **5.1 Inclusion Criteria**

Participants are eligible to be included in the study only if **all** of the criteria below apply.

1. Participant or legally authorized representative must be able to understand the purpose and risks of the study and provide written informed consent and authorization to use protected health information (in accordance with national and local patient privacy regulations).

2. Male or female participants at least 18 years of age at the time of signing the informed consent.
3. Participants who are hospitalized with coronavirus (SARS-CoV-2) infection, confirmed by PCR test or other commercial or public health assay in any specimen, as documented by either of the following:
  - a) PCR positive in sample collected < 72 hours prior to first dose, OR
  - b) PCR positive in sample collected  $\geq$  72 hours prior to first dose (but no more than 14 days prior to first dose), documented inability to obtain a repeat sample (eg, due to lack of testing supplies, limited testing capacity, results taking > 24 hours, etc), AND progressive disease suggestive of ongoing SARS-CoV-2 infection.
4. Evidence of respiratory failure attributable to COVID-19 pneumonia (documented radiographically) before enrollment where respiratory failure is defined based on resource utilization of any of the following modalities:
  - a) Endotracheal intubation and mechanical ventilation.
  - b) Oxygen delivered by high-flow nasal cannula (heated, humidified, oxygen delivered via reinforced nasal cannula at flow rates > 20 L/min with fraction of delivered oxygen  $\geq$  0.5).
  - c) Noninvasive positive pressure ventilation or continuous positive airway pressure.
  - d) Extracorporeal membrane oxygenation.
5. Nasogastric tube or other types of oral or percutaneous gastric feeding tube; placement must be radiographically confirmed and expected to remain in place, as judged by the Investigator, for a minimum of 3 days after study enrollment.
6. Has received treatment with PPIs (eg, omeprazole, esomeprazole, lansoprazole, dexlansoprazole, rabeprazole, or pantoprazole) for a minimum of 24 hours immediately prior to enrollment; any PPI will be permitted, provided it meets the minimum equivalent daily dose of 20 mg rabeprazole.
7. Willing to follow contraception guidelines when discharged from the hospital (Appendix F).

## 5.2 Exclusion Criteria

Participants are excluded from the study if **any** of the criteria below apply.

### Medical Conditions

1. Any serious and uncorrectable medical condition or abnormality of clinical laboratory tests that, in the Investigator's judgment, precludes the participant's safe participation in and completion of the study.
2. Suspected uncontrolled active bacterial, fungal, viral, or other infection (besides infection with SARS-CoV-2).

3. In the opinion of the Investigator, progression to death is imminent and inevitable within the next 24 hours, irrespective of the provision of treatments.
4. Current refractory nausea and vomiting, malabsorption syndrome, disease significantly affecting gastrointestinal function, resection of the stomach, extensive small bowel resection that is likely to affect absorption, symptomatic inflammatory bowel disease, partial or complete bowel obstruction, or gastric restrictions and bariatric surgery, such as gastric bypass.
5. Pregnant or breastfeeding.
6. Uncontrolled or untreated symptomatic arrhythmias, myocardial infarction within the last 6 weeks, or congestive heart failure (New York Heart Association Grade 3 or 4).  
Exception: Participants with controlled, asymptomatic atrial fibrillation during screening are allowed to enroll on study.
7. History of stroke or intracranial hemorrhage within 2 months of study intervention.
8. History of primary immunodeficiency, tuberculosis, PML, aspergillus or other invasive mold/fungal infection, or received organ or bone marrow transplantation within 6 months of enrollment.
9. Known active hepatitis B or C infection as determined by active treatment, medical history or any routine clinical or laboratory evidence that, in the judgement of the Investigator, suggests chronic or active viral hepatitis.  
NOTE: Any participant who does not meet this criterion and for whom hepatitis serology data are not available prior to the first dose, can start treatment, provided they 1) do not have a medical history of HBV or HCV infection, 2) there is no clinical or laboratory evidence to suggest chronic or active viral hepatitis, and 3) blood samples for all HBV and HCV serology and viral load tests (HBV DNA PCR and HCV RNA PCR) are collected prior to the first dose. Refer to guidance in Section 8.2.5.1.1 on how to manage viral hepatitis testing.
10. Known human immunodeficiency virus with viral load and CD4 counts  $< 500$  cells/mm^3.
11. Participants who are unable to undergo multiple venipunctures because of poor tolerability or lack of easy venous access.

### **Laboratory Assessments**

12. Alanine aminotransferase, AST and/or TBL  $\geq 3 \times$  ULN and/or severe hepatic impairment (Child-Pugh class C; see Appendix G) detected during the screening period (per local laboratory).  
Exception: AST and/or ALT can be up to  $5 \times$  ULN if considered due to underlying COVID-19 disease, but cannot be associated with concurrent elevated bilirubin (up to  $2 \times$  ULN).
13. Absolute neutrophil count  $< 500/\mu\text{L}$  at screening (per local laboratory).

14. Platelet count < 50,000/ $\mu$ L at screening (per local laboratory).
15. Estimated creatinine clearance of < 10 mL/min calculated using the Cockcroft-Gault formula  $[(140 \times \text{age}) \times \text{mass (kg)}] / (72 \times \text{creatinine mg/dL})$  multiply by 0.85 if female].

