## **6.6.1 Acalabrutinib Dose Modifications in Special Populations**

### **6.6.1.1 Renal Impairment**

After administration of a single 100 mg radiolabeled acalabrutinib dose in healthy participants, 84% of the dose was recovered in the feces and 12% of the dose was recovered in the urine (2% acalabrutinib). No clinically relevant PK difference was observed in participants with mild or moderate renal impairment (eGFR  $\geq 30$  mL/min/1.73 m^2, as estimated by MDRD equation). Acalabrutinib PK and clinical safety has not been evaluated in participants with severe renal impairment (eGFR  $< 29$  mL/min/1.73 m^2, MDRD) or renal impairment requiring dialysis.

The effect of dialysis on acalabrutinib plasma concentrations has not been studied. Acalabrutinib is rapidly absorbed, metabolized, and distributed. The plasma-protein binding is 97.5% and is noncovalent (potentially dialyzable). However, acalabrutinib covalently binds to the target, BTK, and will not be dialyzable. As such, it is unlikely that a clinically meaningful lowering of total BTK occupancy in target cell populations will be impacted. If participants with COVID-19 enrolled in this study require acute hemodialysis, it is recommended to dose acalabrutinib 100 mg and pause hemodialysis for 2 to 4 hours after acalabrutinib administration to allow for absorption and distribution to target cell populations.

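### Exclusion criterion 15 shows the Cockcroft-Gault formula with 140 multiplied by age; evaluated that way, no plausible creatinine reaches the < 10 mL/min cut-off

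*Protocol*

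**What the plan says.** Section 5.2 of the protocol opens with the rule that "Participants are excluded from the study if any of the criteria below apply". Under Laboratory Assessments, criterion 15 sets the renal limit: "Estimated creatinine clearance of < 10 mL/min calculated using the Cockcroft-Gault formula". The formula follows in brackets. In the machine-read text its numerator begins "140 \times \text{age}) \times \text{mass (kg", where \times stands for a multiplication sign. The denominator is 72 times creatinine in mg/dL, and the instruction ends "multiply by 0.85 if female".

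The formula is written out nowhere else in the protocol, so no other section confirms or corrects it. Neither amendment log lists a change to criterion 15.

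Two other places bear on it. Section 5.1 sets the youngest eligible age: "Male or female participants at least 18 years of age at the time of signing the informed consent". Section 6.6.1.1 says that "Acalabrutinib PK and clinical safety has not been evaluated in participants with severe renal impairment", which it defines as an eGFR below 29 mL/min/1.73 m² by the MDRD equation. It puts mild or moderate impairment at 30 or above on the same measure.

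**The concern.** The criterion compares a calculated value with a fixed cut-off, so the expression has to give values on the scale of that cut-off. With 140 multiplied by age it does not: the result is far too large, and it increases with age when weight and creatinine are held fixed.

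At stake is whether the rule can work if someone follows it literally. It is the only numeric renal limit among the eligibility criteria. Section 5 allows no waivers, and Section 8 requires sites to confirm that every criterion is satisfied, so each criterion should be computable from its own text. Renal failure is foreseeable in this population: category 7 of the ordinal scale (Table 8) includes renal replacement therapy, and Section 6.6.1.1 provides for acute hemodialysis.

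**Working it through.** **Inputs from the protocol.** Cut-off 10 mL/min, constants 140 and 72, and female factor 0.85 (criterion 15); minimum age 18 years (Section 5.1). The protocol gives no worked clearance value, so there is no stated result to reproduce. The ages above 18, the weights and the creatinine values below are illustrative assumptions.

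**Formulas** (F = 0.85 for women, 1 for men; age in years, weight in kg, creatinine in mg/dL):
- As shown: 140 × age × weight × F / (72 × creatinine)
- Named formula: (140 − age) × weight × F / (72 × creatinine)

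**Step 1: clearance in example participants (mL/min).**

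| Participant | As shown | With 140 − age |
|---|---|---|
| Man, 60 y, 80 kg, creatinine 1 | 672,000/72 = 9,333 | 6,400/72 = 88.9 |
| Man, 60 y, 80 kg, creatinine 9.5 | 672,000/684 = 983 | 6,400/684 = 9.4 |
| Woman, 70 y, 70 kg, creatinine 8 | 583,100/576 = 1,012 | 4,165/576 = 7.2 |
| Woman, 18 y, 40 kg, creatinine 15 | 85,680/1,080 = 79 | 4,148/1,080 = 3.8 |
| Woman, 18 y, 30 kg, creatinine 30 | 64,260/2,160 = 29.8 | 3,111/2,160 = 1.4 |

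The last four would be excluded under the named formula. None would be excluded under the expression as shown. The first row shows the problem from the protocol alone: a man with creatinine 1 mg/dL gets 9,333 mL/min, while Section 6.6.1.1 grades renal function around a boundary of about 30. That boundary is on a different measure (MDRD eGFR), but the order of magnitude is comparable.

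**Step 2: creatinine above which clearance falls below 10 mL/min.** Setting the result to 10 gives creatinine = numerator / 720.

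| Participant | As shown (mg/dL) | With 140 − age (mg/dL) |
|---|---|---|
| Woman, 18 y, 30 kg | 64,260/720 = 89 | 3,111/720 = 4.3 |
| Woman, 18 y, 40 kg | 85,680/720 = 119 | 4,148/720 = 5.8 |
| Man, 60 y, 80 kg | 672,000/720 = 933 | 6,400/720 = 8.9 |
| Woman, 85 y, 50 kg | 505,750/720 = 702 | 2,337.5/720 = 3.2 |

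**Step 3: the same result without assuming a weight or creatinine.** Weight, creatinine and sex cancel in the ratio of the two expressions, which is 140 × age / (140 − age).
- Age 18: 2,520/122 = 20.7
- Age 60: 8,400/80 = 105
- Age 85: 11,900/55 = 216

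A cut-off of 10 on the expression as shown therefore corresponds to a Cockcroft-Gault clearance of 10/20.7 = 0.48 mL/min at age 18 and 10/105 = 0.095 mL/min at age 60. The ratio grows with age, so 0.48 mL/min is the highest effective cut-off any eligible adult could face.

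**The case against.** **The sign may not be the sponsor's.** The text was read from PDF by a program, and the brackets around this formula do not balance: one square bracket opens and two close. A minus sign read as a multiplication sign, next to two genuine ones, is possible. Against that, minus signs survive elsewhere in the same text, for example in the screening column of Table 1. This part of the objection stands: the source page has to be checked before anything is changed.

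**The named method governs.** Criterion 15 asks for Cockcroft-Gault, and the bracket only spells it out. A site using a standard calculator gets the right value, and a site that computed 9,333 mL/min would probably notice. This also stands, and it makes the harm conditional. A reader might infer that the trial admits everyone the criterion was meant to keep out. The protocol does not support that: it does not say which expression the sites, the eCRF or any screening tool uses, and criterion 1 still lets the investigator exclude for a serious condition or laboratory abnormality.

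**It is not literally impossible to meet.** A reader might say that the criterion can never be satisfied. Strictly it can, at a creatinine of about 89 mg/dL or more in the smallest example above. The claim is about plausible values, not algebra.

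**The wider consequences are thin.** A reader might infer a material effect on PK variability. Section 6.6.1.1 reports 12% of the dose recovered in urine, 2% as acalabrutinib, which gives that little support. Nor does the operator create the gap in evidence on severe renal impairment. With the correct sign, a cut-off of 10 mL/min still admits most of the range below 29, allowing for the difference between the two measures.

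What remains is that an operative eligibility rule, if the text is faithful, gives an expression that cannot do the job of its own cut-off.

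**Conclusion.** The point holds in a limited form. As it reads, the expression in criterion 15 is not the formula the criterion names. It overstates clearance by a factor of about 21 at age 18 and 105 at age 60, so the < 10 mL/min exclusion is out of reach at any plausible creatinine.

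This rests on two conditions: that the multiplication sign is on the source page, and, for any practical effect, that someone has used or programmed the written expression in place of a standard calculator. If both are true, the only numeric renal limit excludes nobody and criterion 1 is the remaining safeguard. If only the first is true, it is a misprint in an eligibility criterion that should still be corrected. If the first is false, there is nothing to correct in the protocol.

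No endpoint, sample size or analysis depends on it. No view is taken on whether 10 mL/min is the right threshold.

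**What to change.** 1. Check criterion 15 on the source page. If it shows 140 minus age, close the point.
2. If it shows a multiplication sign, correct the expression at the next amendment to (140 − age) × mass (kg) / (72 × creatinine in mg/dL), times 0.85 if female, and leave the threshold as it is.
3. Send sites a short clarification now, ahead of the amendment.
4. Confirm which expression any eCRF derivation or screening worksheet uses. Only if it is the printed one, recompute clearance for the participants already enrolled.

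The cost is one operator, one site note and one programming check. Any recomputation covers at most the approximately 20 planned participants and uses age, weight and serum creatinine, all collected at screening under Table 1.

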### **Prior/Concomitant Therapy**

16. Treatment with a strong CYP3A inhibitor (within 7 days before first dose of study intervention) or inducer (within 14 days before first dose of study intervention).
17. Received BTK inhibitor within 7 days before enrollment.
18. Requires or is receiving specific anticoagulation with warfarin or equivalent vitamin K antagonists (eg, phenprocoumon) within 7 days prior to enrollment. Other anticoagulants are permitted.
19. Participants on dual antiplatelet **and** therapeutic/high-dose anticoagulant therapy (eg, aspirin and therapeutic/high doses of low-molecular-weight heparin are not allowed; however, aspirin and prophylactic/low doses of low-molecular-weight heparin are allowed).
20. History of hypersensitivity (ie, allergic response) to active or inactive excipients of acalabrutinib or other BTK inhibitors.
21. Known cytoreductive chemotherapy treatment within 14 days of enrollment.

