## **6.5 Concomitant Therapy**

Any medication or vaccine (including over-the-counter or prescription medicines, vitamins, and/or herbal supplements or other specific categories of interest) that the participant is receiving at the time of enrollment or receives during the study must be recorded along with:

- Reason for use
- Dates of administration including start and end dates
- Dosage information including dose and frequency

The Study Physician should be contacted if there are any questions regarding concomitant or prior therapy.

The Investigator must be informed as soon as possible about any medication taken from the time of screening until the end of the clinical treatment phase of the study including the 28-day follow-up period following the last dose of study intervention.

Best supportive care should be entered as a concomitant medication in the eCRF.

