#### **Medications Prohibited Through Day 14**

**Strong CYP3A inhibitors or inducers:** Drug-drug interactions may occur with some of the drugs being used as BSC (eg, drugs that are strong inducers or strong inhibitors of CYP3A). Concomitant administration with a strong inhibitor of CYP3A has the potential to increase

acalabrutinib exposure. Conversely, concomitant administration with a strong inducer of CYP3A has the potential to decrease exposure of acalabrutinib and could reduce efficacy. Therefore, the concomitant use of strong inhibitors or inducers of CYP3A (see Appendix E) should be avoided in the study. If a participant requires a strong CYP3A inhibitor or inducer while on treatment with acalabrutinib, acalabrutinib treatment must be discontinued. Refer to Section 6.5.4 for additional information on drugs with potential drug-drug interactions.

**Other BTK inhibitors:** BTK inhibitors other than acalabrutinib are prohibited.

**Certain anticoagulants:** Warfarin or equivalent vitamin K antagonists (eg, phenprocoumon) are prohibited in the study. Participants who require prophylaxis or therapeutic anticoagulation for thrombosis (deep vein thrombosis or pulmonary embolism) will be allowed to receive therapeutic anticoagulation with a non-vitamin K inhibitor class of anticoagulants (eg, heparin or low-molecular-weight heparin).

Refer to Section 5.2 for additional restrictions on concomitant therapy.

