**Table 7 Guidelines for Acalabrutinib Dose Modification or Discontinuation**

Event	Acalabrutinib Dose Modification/Discontinuation
Hematological	
Grade 4 neutrophil count decrease (ANC < 500/ $\mu$ L)	
 
• Hold acalabrutinib, and consider introducing growth factors (eg, G-CSF) and continue to monitor ANC
 
• If neutropenia has improved to Grade 1 or baseline within 3 days of event onset, restart acalabrutinib
 
• If neutropenia has not improved to Grade 1 or baseline within 3 days of event onset, discontinue acalabrutinib
 

Any grade febrile neutropenia lasting more than 2 days	
 
• Discontinue acalabrutinib
 
• Consider introducing growth factors (eg, G-CSF), evaluate participant for infection, and begin antibiotic treatment per institutional guidelines
 

Presence of significant bleeding events with or without thrombocytopenia, such as: 
 
• Grade 3 or 4 hemorrhage
 
• Any grade serious hemorrhage event
 
• Any grade intracranial hemorrhage or hematoma
 
	Discontinue acalabrutinib

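### Exclusion criterion 19 states its rule as dual antiplatelet therapy plus therapeutic anticoagulation, but its example bars aspirin alone, leaving a single non-aspirin antiplatelet undecided

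*Protocol*

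**What the plan says.** Criterion 19 in Section 5.2 of the Protocol, under Prior/Concomitant Therapy, opens with "Participants on dual antiplatelet". A bold *and* joins this to "therapeutic/high-dose anticoagulant therapy (eg, aspirin and therapeutic/high doses of low-molecular-weight heparin are not allowed". The same bracket then gives the contrasting permitted case: "however, aspirin and prophylactic/low doses of low-molecular-weight heparin are allowed". Neither the criterion nor the abbreviation list in Appendix I defines the antiplatelet term.

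Criterion 18, just above, excludes vitamin K antagonists and permits other anticoagulants without mentioning antiplatelets.

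For treatment on study, Section 6.5.3 (Certain anticoagulants) says that participants who need anticoagulation for thrombosis "will be allowed to receive therapeutic anticoagulation with a non-vitamin K inhibitor class of anticoagulants (eg, heparin or low-molecular-weight heparin"). It does not mention antiplatelet agents. It closes with: "Refer to Section 5.2 for additional restrictions on concomitant therapy".

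Two general rules bear on how the criterion is applied. Section 5 says: "Prospective approval of protocol deviations to recruitment and enrollment criteria, also known as protocol waivers or exemptions, is not permitted". Section 6.5 says: "The Study Physician should be contacted if there are any questions regarding concomitant or prior therapy".

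**The concern.** An exclusion criterion should give every site the same answer for the same patient. Here the rule and its example give different answers on the usual reading of the rule. A site that takes dual antiplatelet to mean two agents would enroll a patient on clopidogrel alone with therapeutic LMWH. A site that reasons from the example would exclude that patient. The first site would see no question to raise, so the route to the Study Physician would not be used.

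The criterion guards against adding a BTK inhibitor to an antiplatelet agent and full-dose anticoagulation. Hemorrhage, including fatal events, is a listed risk of acalabrutinib (Section 2.3.1.1). What is at stake is consistent eligibility and bleeding safety.

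**Working it through.** No arithmetic applies, and the protocol has no figure of its own to reproduce here. The check applies two readings of criterion 19 to the relevant combinations, then looks for other text that decides between them.

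- Reading A (usual meaning): two antiplatelet agents plus a therapeutic anticoagulant are barred.
- Reading B (logic of the example): any antiplatelet agent plus a therapeutic anticoagulant is barred. On this reading, dual refers to the pairing of one antiplatelet with one anticoagulant.

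| Combination | Reading A | Reading B | Decided by the printed text? |
|---|---|---|---|
| Two antiplatelets + therapeutic anticoagulant | Barred | Barred | Yes, barred |
| Aspirin alone + therapeutic LMWH | Admitted | Barred | Yes, barred: named in the example |
| Aspirin alone + therapeutic unfractionated heparin | Admitted | Barred | Probably barred, by analogy with a non-exhaustive example |
| Another single antiplatelet + therapeutic anticoagulant | Admitted | Barred | No |
| Aspirin alone + prophylactic LMWH | Admitted | Admitted | Yes, allowed: named in the example |
| Two antiplatelets + prophylactic anticoagulant | Admitted | Admitted | Not barred by this criterion |
| Therapeutic non-vitamin K anticoagulant alone | Admitted | Admitted | Yes, allowed: criterion 18 and Section 6.5.3 |

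The readings part only where one antiplatelet meets therapeutic anticoagulation. Within that group, aspirin with LMWH is settled and aspirin with heparin nearly so. The case left without an answer is the single non-aspirin antiplatelet.

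Other text does not close the gap:

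- Criterion 18 permits other anticoagulants without an antiplatelet condition. If anything, it pulls toward admission.
- Section 6.5.3 allows therapeutic heparin or LMWH on study and adds only a general pointer to Section 5.2, so the unclear wording of criterion 19 is carried into the treatment period.
- The Amendment 2 summary of changes describes the revision of criterion 19 only through the aspirin and LMWH pair. That supports Reading B as the intent but does not restate the rule.

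A foreseeable on-study sequence shows the gap. A participant enters on clopidogrel with prophylactic LMWH, which neither reading bars, and then develops a deep vein thrombosis. Section 6.5.3 allows therapeutic anticoagulation. Whether the antiplatelet may continue depends on criterion 19, and no action is given if it may not. By contrast, the paragraph on strong CYP3A inhibitors and inducers in Section 6.5.3 does give an action: acalabrutinib must be stopped.

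**The case against.** The strongest reply is that the criterion, read as a whole, is coherent. The *and* is in bold, the barred example pairs one antiplatelet with one anticoagulant, and both examples hold aspirin fixed and change only the heparin dose. Anticoagulant intensity is then the deciding factor, and Reading B is what the sponsor meant. This stands as evidence of intent, and the fix follows it. It does not make the text clear, because dual is attached to antiplatelet, the phrase has a settled usual meaning, and nothing in the protocol redefines it.

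A second reply is that other safeguards limit the consequence. Criterion 1 leaves room for investigator judgment, criterion 7 excludes recent stroke or intracranial hemorrhage, and criterion 14 sets a platelet floor. Coagulation tests are run every other day in hospital. Table 7 stops the drug for "Presence of significant bleeding events with or without thrombocytopenia", and the Safety Review Committee meets on any Grade 4 hemorrhage that the investigator attributes to acalabrutinib. The ban on waivers does not prevent a site from asking what a criterion means. All of this stands and keeps the point modest. Still, Table 7 and the committee act only after a bleed, and the Study Physician helps only a site that sees a question.

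Two stronger inferences are tempting, and the documents do not support them:

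- A reader might infer that most single-antiplatelet combinations are undecided and put a fraction on it. Any such fraction depends on how the reader divides the cases, and it treats an example marked *eg* as a complete list.
- A reader might use Table 2 to size the harm: major hemorrhage in 37 of 1040 participants (3.6%), Grade 3 or higher in 28 (2.7%). Those participants had hematologic malignancies and long-term treatment, and the median time to a first major hemorrhage was 9.8 months (range 0 to 44). Dosing here is 14 days, with at most 28 doses, and Section 2.3.1 itself says that the safety profile may differ in COVID-19. The rates show that hemorrhage is a listed risk. They do not measure the effect of this wording.

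**Conclusion.** The point holds in a narrow form. Rule and example in criterion 19 conflict on the usual meaning of dual antiplatelet, and no other text resolves the conflict. The clearly open case is a single non-aspirin antiplatelet with a therapeutic anticoagulant, both at entry and, through the pointer in Section 6.5.3, on study.

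This rests on two assumptions: that sites will tend to read the phrase in its usual sense, and that the general pointer to Section 5.2 is meant to carry criterion 19 into the treatment period. No percentage or participant number is attached, since the protocol gives no prevalence of antiplatelet or anticoagulant use among the approximately 20 participants planned. The PK, sample size and efficacy analyses are not affected. It is a contradiction in a bleeding-safety exclusion, cheap to remove and worth removing.

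**What to change.** In criterion 19, replace *dual antiplatelet* with *any antiplatelet agent (including aspirin alone)* and keep both examples, which then agree with the rule. If the sponsor did mean two antiplatelet agents, keep the rule and correct the example instead.

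In Section 6.5.3, Certain anticoagulants, add two statements:

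- The combination restriction of criterion 19 applies for as long as acalabrutinib is given, including any dosing after Day 14. This needs saying because the paragraph sits under a heading that ends at Day 14, while Section 6.1.2.3 lets missed doses be completed beyond the 14-day period.
- A participant who comes to need therapeutic anticoagulation must stop the antiplatelet agent or discontinue acalabrutinib.

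The cost is a protocol amendment with the usual ethics and regulatory approval, and possibly slightly narrower eligibility if some sites have been reading the rule literally. No new data collection is needed.
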